- Discussion of removal of means, including firearms
- Increased frequency of visits
- Phone check ins between sessions and upon missed appointment

For those at high risk, the following will be considered based on clinical judgment:

- Referral to high risk treatment program, such as DBT

- Emergency room (voluntary)
- Emergency room (involuntary)

For those who present with elevated risk at termination, we will offer:

- Referral to alternate or high risk treatment programs, as indicated

Blood-drawing: Proper sterile techniques will minimize the rare risk of infection.

Audiotaping: The purpose of the audiotaping will be explained, confidentiality will be respected, and tapes will be erased after the spot checks or following supervision. Informed consent for taping will be obtained.

Other Procedures for Minimizing Risk:

- 1) Careful medical and psychiatric screening to identify patients for whom risk for potential adverse effects are elevated. Such patients will be excluded from the study. As an example, an actively suicidal patient would be excluded from study participation and appropriate clinical treatment provided.
- 2) Patients with any of the following will be removed from research and treated openly or as clinically indicated: a) the occurrence of assaultive or illegal behavior; b) the occurrence of active suicidal ideation at any point during the trial as assessed by clinical interview; c) behaviors while intoxicated that are a danger to him/herself or others.
- 3) Inclusion of psychoeducation about PTSD, the treatment process and memory triggers within the therapeutic framework.
- 4) Careful monitoring of patients during pretreatment and study participation by experienced clinicians. Patients will see the same clinicians for each of their treatment visits.
- 5) Ability to remove any patient from the study who evidences significant clinical deterioration during acute treatment. Provisions will be made for appropriate clinical care of such patients.
- 6) Patients failing to benefit from the study treatment will be exited from the study and provided with appropriate clinical care based on weekly review with termination criteria (see section 4A.7).
- 7) All data will be coded and stored in locked files to insure confidentiality.

Methods to Protect Confidentiality

Describe methods to protect confidentiality

All data collected will be kept confidential and used for research purposes only. Patient charts will be kept in locked file cabinets identified by number. Access to research records is restricted to research staff and Federal, State, and Institutional regulatory authorities. Electronic data will be protected by password access. No subject's identifying data will be published.

MRI: The results of the structural MRI will be shared with the subject and/or a physician of their choice, as detailed below. Because the structural MRI scan is being performed for research purposes only it may not show problems that would normally be found in a typical clinical MRI scan ordered by a doctor for a specific medical problem. The MRI scans obtained in this study may provide information that is clinically

relevant. The quality of clinical information available from these images can vary widely, based on resolution, degree of motion artifact, and numerous aspects of the pulse sequences used to acquire them. All scans will be read by a clinical neuroradiologist (see “Personnel and Responsibilities”). As with any imaging procedure, if the radiologist determines that the quality of the scan does not lend itself to a clinical reading, he or she will provide written documentation to this effect. Only the radiologist may make this determination.

The MRI will receive a clinical reading by a neuroradiologist within 4 weeks of the scan, and a confirmatory report will be written within 6 weeks of the scan as the following details. When the readings yield findings that are of urgent clinical concern, the radiologist (see “Personnel and Responsibilities”) will immediately provide an oral report followed by a handwritten or typed note to the co-investigator, [name], and the Director of the MRI Center. A final written transcript of the clinical reading will be provided within two weeks of the oral report. The radiologist will provide routine written reports to [name], PhD, within one month of image acquisition. Because T1 images are acquired in this study, all subjects will receive feedback about their scans in accordance with IRB policy. All results will be shared with research subjects in a manner that is consistent with the acuity and certainty of the finding, and will be communicated by an appropriately qualified member of the research team in the form of a letter that is approved by the IRB and will also be contacted by telephone if there is evidence of a clinically-significant abnormality. Results will be shared with the subject and/or a physician designated by the subject.

Will the study be conducted under a certificate of confidentiality?

No

Direct Benefits to Subjects

Direct Benefits to Subjects

All participants will receive a complete psychiatric evaluation and medical evaluation, results of which will be communicated to the participant’s and their physician, at the participant’s request. PTSD and MDD symptoms may improve as a result of the PE and pramipexole treatment, but patients will receive no direct benefit from fMRI or other study procedures. A potential benefit to society of this research is that the knowledge gained may provide future benefits for individuals with PTSD-MDD in terms of improved understanding of brain function in PTSD-MDD, which may improve future treatments.

Compensation and/or Reimbursement

Will compensation or reimbursement for expenses be offered to subjects?

Yes

Please describe and indicate total amount and schedule of payment(s).

Include justification for compensation amounts and indicate if there are bonus payments.

Study participants will receive \$100.00 for the completing the first MRI visit (\$16.20 for completion of the Probabilistic Reward Task, \$20 for completion of the self-report tasks and \$63.80 for completion of the MRI), \$100 for completing the second MRI visit (\$16.20 for the Probabilistic Reward Task \$20 for completion of the self-report tasks and \$63.80 for completion for the MRI). Participants will receive 30\$

for completion of the midpoint evaluation (clinician assessment and self-report forms). Participants will also receive an additional \$50 for completing the 3-month follow up (clinician assessment and self-report forms). Study patients will receive up to a total of \$280 for their participation in the study. Compensation will be pro-rated if the subject does not complete all the study procedures. Payments to subjects will be in the form of a check payable by RFMH mailed to the participant within 4-6 weeks of the end of the subject's study participation.

References

References

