cartoon face. The task includes three blocks of 100 trials. The difference between mouth sizes presented as well as the duration of stimulus exposure (100ms) is small, providing a setting in which a response bias may develop in response to asymmetric reinforcement: either the short or long mouth is rewarded (“Correct!! You won 20 Cents”) three times more frequently (“rich stimulus”) than correct identification of the other mouth (“lean stimulus”). In each block, only 40 correct trials (30 rich, 10 lean) are rewarded, so each subject is exposed to the same reward ratio. Subjects are informed that the purpose of this task is to win as much money as possible. Moreover, they are instructed that not all correct response will receive a reward feedback but they will be unaware that one of the stimuli will be disproportionately rewarded. Performance will be analyzed with respect to response bias, discriminability, and reaction time (RT), following prior procedures. This task will take approximately 25 minutes.

Attention Allocation Task: In each trial subjects will be shown a stimuli matrix containing 16 images, 6 negative and 6 neutral, for 6 seconds. The task is comprised of two 30 trial blocks. Participants will be asked to view the different image matrices freely with no specific instructions while being recorded by an eye-tracking apparatus collecting eye-movement data. Eye-tracking recording does not pose any danger or harm for participants. The task will take approximately 20 minutes.

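### Do the attention-display image counts and the reward-task winnings, which do not match the totals given elsewhere, require a change to the plan?

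*Combined protocol and SAP*

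**What the plan says.** All the task detail is in the Study Procedures section of the combined protocol and SAP, in the paragraphs on the two behavioural tasks.

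- **Attention Allocation Task.** The display is described as follows: "In each trial subjects will be shown a stimuli matrix containing 16 images, 6 negative and 6 neutral, for 6 seconds". On length, "The task is comprised of two 30 trial blocks". Patients view the images freely while their eye movements are recorded. No gaze index, chance value or test is named.
- **Probabilistic Reward Task.** "The task includes three blocks of 100 trials". On rewards, "In each block, only 40 correct trials (30 rich, 10 lean) are rewarded, so each subject is exposed to the same reward ratio". The feedback on a rewarded trial is "You won 20 Cents". Patients also receive an instruction: "Subjects are informed that the purpose of this task is to win as much money as possible". The named measures are response bias, discriminability and reaction time, scored as in earlier work.
- **Compensation and/or Reimbursement.** The breakdown for the first MRI visit lists, in dollars, "16.20 for completion of the Probabilistic Reward Task". The same amount is listed for the second MRI visit.

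Section 4.A.5 (Follow up visit) repeats the behavioural tasks after treatment and describes the procedures as the same as in the first session. The hypothesis under Specific Aims and Hypotheses covers PTSD symptoms, depressive symptoms and functional connectivity. It mentions neither task.

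**The concern.** The attention sentence contradicts itself: the two named image types fill 12 places in a 16-place display. No other section describes the display, so the text cannot settle which number is wrong. If gaze on negative images were judged against the share expected with no preference, that share would depend on the counts, and a wrong count would misplace the reference.

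In the reward task, the wins shown on screen can add up to more than the sum paid. Patients are told to win as much as they can and do the task twice. Someone who noticed that displayed wins are not what is paid might respond differently at the second session, when the treatment effect is read.

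**Working it through.** **Attention display**

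Inputs (Attention Allocation Task paragraph): 16 images, 6 negative, 6 neutral, two blocks of 30 trials, 6 seconds per trial.

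1. Stated types: 6 + 6 = 12. Unaccounted for: 16 - 12 = 4, and 4/16 = 25% of the display.
2. Duration: 2 x 30 = 60 trials and 60 x 6 s = 360 s = 6 minutes of viewing. This fits within the stated 20 minutes or so, so the fault is confined to the image counts.
3. No-preference share of gaze on negative images, by reading:

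| Reading | Negative / all images | Negative / (negative + neutral) |
|---|---|---|
| 6 and 6 in a 12-image display | 6/12 = 50% | 6/12 = 50% |
| 8 and 8 in a 16-image display | 8/16 = 50% | 8/16 = 50% |
| 6, 6 and 4 of another type | 6/16 = 37.5% | 6/12 = 50% |
| 6 negative, 10 neutral | 6/16 = 37.5% | 6/16 = 37.5% |
| 10 negative, 6 neutral | 10/16 = 62.5% | 10/16 = 62.5% |

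The first three readings keep the stated six-and-six or an even split. For these, the gap of 50 - 37.5 = 12.5 points arises only when gaze on unnamed images enters the denominator. With the usual two-category share, all three give 50%. The last two readings require one stated count to be wrong and the split to be uneven.

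4. Effect on the pre/post comparison. Let B and P be a patient's share at baseline and after treatment, and c the reference value. The change in bias is (P - c) - (B - c) = P - B. The reference cancels whatever its value, provided the display is the same at both sessions, as section 4.A.5 indicates.

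**Reward task**

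Inputs: 3 blocks, 40 rewarded correct trials per block (30 + 10), 20 cents each, $16.20 paid.

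1. Reward ratio: 30/10 = 3, as the paragraph states. The task's own counts agree.
2. Maximum displayed winnings: 3 x 40 x $0.20 = $24.00.
3. The payment expressed as rewards: $16.20 / $0.20 = 81, or 81/3 = 27 per block. Two blocks would give 2 x 40 x $0.20 = $16.00. No stated schedule yields $16.20.
4. Largest gap: $24.00 - $16.20 = $7.80 per session (7.80/24.00 = 32.5%), or $15.60 over two sessions.
5. The payment figures agree among themselves: $16.20 + $20 + $63.80 = $100 per MRI visit, and $100 + $100 + $30 + $50 = $280 in total.

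The $24.00 is a ceiling, because only correct responses are rewarded. What the paragraph holds constant across patients is the ratio of rich to lean rewards, not the sum won.

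**The case for a change.** The best case for a change is that the attention task is in active use and is the subject of the current amendment, which adds two exclusions (ADHD and calibration difficulty) for this task alone. It seems odd to protect a measure from confounding while leaving its stimulus unclear. The reward task has its outcome measures named and the attention task has none. Correcting both paragraphs would cost almost nothing.

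Part of this stands. The sentence is wrong or incomplete as written, and an outside group could not rebuild the display from it. Nobody, however, can score gaze on negative images without knowing which images were negative, so the analyst must take the composition from the task program in any case. Naming a gaze measure would help a reader, but its absence is missing detail on a task outside the stated hypothesis.

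The reward-task argument is weaker. The payment is described as "for completion of the Probabilistic Reward Task", and no section says that it equals the winnings or that winnings are paid out. The experimental manipulation is the 3:1 reinforcement schedule; the amount is 20 cents for either stimulus, and the visit payment leaves that schedule untouched. Changing the number of rewarded trials or the amount per trial to match the payment would alter a task that is to be scored by established procedures. The possibility that patients learn between sessions that displayed wins are not paid is conjecture. The consent pages are not in the available file, so what patients are told about payment cannot be judged.

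**Conclusion.** No change to the plan follows. The attention display has a clerical slip or an incomplete description: 4 of 16 images have no stated type. The possible 12.5-point shift applies to a reference value that the plan does not use. It vanishes under a negative-versus-neutral share with equal counts, and it cancels from the pre/post change under any counts. The reward-task figures ($24.00 at most shown, $16.20 paid) are two quantities that the plan never sets equal, and the task's internal counts are consistent.

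This rests on two assumptions: that the same display is used at both sessions, as section 4.A.5 indicates, and that the composition can be read from the task program when gaze is scored. If the sponsor edits the section for other reasons, stating the image counts and saying that the $16.20 is a fixed payment would help readers. Neither edit would alter the sample size, the clinical outcomes, the connectivity hypothesis or the reading of either task's change over treatment.

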3. Severe substance use disorder excluding nicotine (i.e., nicotine use disorder and mild-moderate alcohol/cannabis use disorder are accepted)	SCID-V and clinical interview
4. Individuals at risk for suicide based on history and current mental state. BDI-II suicide item $>$ 2 or CGI-Severity baseline score of 7.	HRSD-17, CGI, clinical interview
5. Treatment with antidepressants or other psychotropic medication in the past 4 weeks (or 6 weeks for fluoxetine; an exception will be made for zolpidem used intermittently for sleep).	Clinical interview and history
6. Pregnancy or plans to become pregnant during the period of the study.	Urine β -HCG, clinical interview
7. Current psychotherapy	Clinical interview
8. Current unstable or untreated medical illness	Clinical interview,

	physical exam, blood chemistry
9. Any condition that would exclude clinical MRI exam (e.g. pacemaker, paramagnetic metallic prosthesis, surgical clips, shrapnel, necessity for constant medicinal patch, some tattoos, severe obesity, claustrophobia)	Clinical interview, physical exam, MRI screening questionnaire
10. History of untoward reaction to pramipexole	Clinical interview, history
11. Prior or current diagnosis of OCD, Panic Disorder or Social Phobia	SCID-V and Clinical Interview
12. Medical diagnosis of Parkinson's disease	Clinical Interview, physical exam, blood chemistry
13. Eye tracking calibration difficulties as determined on day of study (Attention Allocation Task participants only)	Calibration procedures
14. Current or past ADHD diagnosis (Attention Allocation Task participants only)	SCID-V and Clinical Interview

Waiver of Consent/Authorization

Indicate if you are requesting any of the following consent waivers
Waiver of consent for use of records that include protected health information (a HIPAA waiver of Authorization)

- No
- Waiver or alteration of consent
- No
- Waiver of documentation of consent
- No
- Waiver of parental consent
- No

Consent Procedures

Is eligibility screening for this study conducted under a different IRB protocol?

Yes

Indicate NYSPI IRB #

7094R

Describe Study Consent Procedures

Research assistant will obtain verbal consent from patient in order to conduct a preliminary phonescreen. Phonescreening will be conducted as part of the Anxiety Disorders Clinic's preexisting screening protocol (IRB #7094R). If the patient will be eligible for the study the RA will invite him for further screening at the clinic.

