At the clinic, patient will meet face to face with a person that is authorized to discuss and document consent (see "person designed to discuss and document consent"). After patient reads the consent the clinician will go over the consent with the patient and answer all the patient's questions. After answering all the patient's questions by the clinician patient will sign the study consent. The highest educational degree needed for the consenting clinician is a Doctor of Medicine degree (M.D.). Throughout this process, the patient will be told that they are free to refuse to participate in the research and that participation or non participation in research has no effect on their ability to continue to receive clinical care or services.

Indicate which of the following are employed as a part of screening or main study consent procedures

✓ Consent Form

Persons designated to discuss and document consent

Select the names of persons designated to obtain consent/assent

[name], MD

[name], MD

[name], MD

Type in the name(s) not found in the above list

Study Procedures

Describe the procedures required for this study

The study consists of the following procedures: 1) screening and diagnostic assessments including: psychiatric interview and medical history, SCID interview, labs and urine drug screen, informed screening consent (3 hrs.); 2) informed study consent, baseline fMRI, behavioral task (2 hours); 3) Ten treatment visits and self-report forms, including CGI (1.5 hours); 4) Midpoint clinical assessment after treatment visit 5 and self-report forms (1 hour) ; 5) Follow up clinical assessment, follow up fMRI and behavioral task (2.5 hours); and 6) 3 month follow up clinical assessment and self-report forms.

4.A1. Preliminary Screening: Potential subjects will be screened by telephone by a research assistant after obtaining oral consent as a part of the Anxiety Disorders Clinic's preexisting screening protocol (IRB #7094R). Patients on prohibited psychoactive medication will be excluded and will not be tapered off such

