medication for the purpose of entering this study. Psychiatric Diagnostic Evaluation: Patients deemed study eligible following preliminary screening will sign the Anxiety Disorders Clinic informed written consent for the psychiatric screening evaluation (IRB # 7094R). An experienced psychiatrist will evaluate presenting symptoms, psychiatric history, treatment history, medical history, trauma history, social and family history, and current medical status. Additional screening measures include: 1) collection of blood samples (20 cc) for chemistry profile, thyroid function tests, and CBC; 2) a urine sample for urinalysis and toxicology (and pregnancy for females); 3) structured interview (the SCID), CAPS-V, HRSD-17, CGI, CVC Suicide Risk Assessment and Screener and TBI performed by trained research team member; 4) a physical exam; 5) self-report forms: PCL-5, LEC-5, BDI-II and SHAPS

After obtaining informed consent and determining eligibility based on the above screening and laboratory testing, study visits will be scheduled.

4.A.2. fMRI Scan: Patients will undergo two fMRI sessions. MRI scans will be performed in the NYSPI 3.0T GE scanner and the 3T Siemens Prisma scanner at Zuckerman Institute MR Center. The scanning session will last approximately 30 minutes, with an additional 30 minutes total for set-up. Thus, the fMRI session lasts about 1 hour. Female subjects will have a urine pregnancy test on the day of the MRI scan, before being scanned. Structural MRI scan will be performed to quantify regional brain volumes and cortical thickness as well as provide a clinical reading by a neuroradiologist to forward results from the scan to the participant. Resting state fMRI will measure functional connectivity.

MRI Results

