Pramipexole. In addition to receiving PE as described above, patients will have Pramipexole treatment administered by our team’s psychiatrists who have expertise in PTSD pharmacotherapy and clinical trials. Initial dosing will follow the methods of [name] (Preliminary Studies 3.3.B.6) and Goldberg (13): Daily dose will be started at 0.25 mg/day and increased by 0.25 mg/day every 3-4 days to a target of 2.5mg day by week 5. Beginning week 6 daily dose will be increased weekly by 0.5 mg/day to a maximum dose of 4mg. Adverse events will be systemically queried at each visit and vital signs will be checked. Compliance will be assessed by weekly pill count. Dose will be increased as tolerated unless the patient has achieved remission and will be decreased in the event of intolerable adverse events. Patients will check in with their treating psychiatrist for 15 minutes after every PE treatment session, for a total of 10 visits, normally conducted once a week (note—make up for missed sessions are allowed within 10-12 week time frame). Patients will see the same psychiatrist for each of their treatment visits. Staff psychiatrists carry beepers or cell phones and are available 24 hours per day for clinical emergencies. Patients will receive written information on how to contact staff by telephone or pager in the event of an emergency.

4.A.4. Midpoint Assessment (week 5): Patients will meet with a clinician and complete CAPS-V, HRSD-17,

CGI, CVC Suicide Risk Assessment and Screener and TBI performed by trained research team member and self-report forms: PCL-5, BDI-II and SHAPS.

4.A.5. Follow up visit: Patients will repeat fMRI scanning session and behavioral tasks. Procedures are identical to the first fMRI session. Follow up medical examinations, including physical exam, blood work, urinalysis will not be done routinely, but will be performed at any time during the study if clinically indicated by occurrence of a specific adverse effect. In addition, patients will complete a follow up assessment with a CAPS-V, HRSD-17, CVC Suicide Risk Assessment and Screener and CGI performed by trained research team member; and self-report forms: PCL-5, BDI-II and SHAPS.

4.A.6. 3 Month follow up visit: Patients will meet with a clinician and complete CAPS-V, HRSD-17, CGI and TBI performed by trained research team member and self-report forms: PCL-5, BDI-II and SHAPS.

You can upload charts or diagrams if any

Criteria for Early Discontinuation

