- a) Pramipexole will be initiated conservatively following procedures of [name] and Goldberg (3) prior studies of depressed patients that resulted in low levels of adverse events. Daily dose will be started at 0.25 mg/day and increased by 0.25 mg/day every 3-4 days to a target of 2.5mg day by week 5. Beginning week 6 daily dose will be increased weekly by 0.5 mg/day to a maximum dose of 4mg. Dosage will be lowered or medication stopped if needed for adverse reactions. Patients will be carefully monitored for signs of daytime drowsiness and warned not to drive while drowsy if this occurs. Adverse events will be inquired about systematically through use of a checklist of side effects previously associated with pramipexole treatment, and vital signs will be assessed at each treatment visit.
- b) Patients will be educated about potential adverse interactions with other medications they may wish to take and advised to contact study physicians before starting new medications.
- c) Careful monitoring of patients weekly during study treatment by experienced clinicians. Patients will see the same clinician for each of their treatment visits. Staff psychiatrists carry beepers or cell phones and are available 24 hours per day for clinical emergencies. Patients will receive written information on how to contact staff by telephone or pager in the event of an emergency. In the event of clinically significant suicidal ideation or a medical or psychiatric emergency in the clinic, patients will be escorted to the emergency room of New York Presbyterian Medical Center, which is adjacent to New York State Psychiatric Institute.
- d) Patients will be instructed to contact study personnel during treatment in the event of worsening of symptoms or significant adverse events. Patients who experience clinically significant worsening (CGI change score > 5) will have study treatment discontinued and will be given appropriate clinical care until stabilized. All patients leaving study treatment will be offered 6 months of free open treatment, after which time they will be referred to appropriate clinical treatment.

- e) Patients will be consented prior to the start of study treatment, and they will be informed that they may withdraw from study treatment at any time.
- f) At the conclusion of study treatment patients discontinuing pramipexole will have it discontinued gradually under supervision.

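### No pregnancy test is scheduled during the 10-12 weeks of pramipexole dosing, and no dose or stop rule covers pregnancy; a midpoint urine test with a drug-handling line would roughly halve the untested interval

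*Combined protocol and SAP*

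**What the plan says.** Exclusion criterion 6 reads "Pregnancy or plans to become pregnant during the period of the study", checked by urine test and interview. It stands apart from criterion 9, which lists the conditions that rule out an MRI.

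After screening, tests are tied to the scans. Section 4.A.2 says: "Female subjects will have a urine pregnancy test on the day of the MRI scan, before being scanned". There are two scan sessions, and 4.A.5 says of the second: "Procedures are identical to the first fMRI session". The MRI paragraphs on risks and on minimizing risks add that the scan will not go ahead if a woman may be pregnant. They say nothing about the drug.

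Dosing runs over ten psychiatrist visits, normally weekly, and "make up for missed sessions are allowed within 10-12 week time frame". The Study Procedures list places a "Midpoint clinical assessment after treatment visit 5 and self-report forms"; 4.A.4 dates it to week 5 and lists only clinician-rated instruments and self-report forms. Treatment visits involve adverse-event queries, vital signs, a pill count and the BDI-II. Under 4.A.5, later physical examination, blood work and urinalysis are not routine but "will be performed at any time during the study if clinically indicated by occurrence of a specific adverse effect".

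On the drug itself, 4.A.3 says: "Dose will be increased as tolerated unless the patient has achieved remission and will be decreased in the event of intolerable adverse events". Item (a) of the pramipexole risk measures lowers or stops the drug for adverse reactions. Item (f) provides a supervised taper, worded for the end of study treatment. None of the five criteria for early discontinuation names pregnancy.

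**The concern.** The plan sets a condition that lasts for the whole study but tests it only at the edges of the treatment period. Followed as written, a woman who becomes pregnant after the baseline scan could stay on pramipexole, including the increases that start in week 6, with no scheduled test until the post-treatment scan. If she stops before that scan, she may have no further scheduled test: the plan enrols 20 to obtain 15 completers, so it allows for 20 - 15 = 5 such patients of either sex.

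If a pregnancy does come to light, the text settles only whether the scan takes place. Whether to hold, reduce, stop or taper the drug, and whether PE goes on, is left open. At stake are participant safety and consistent handling across psychiatrists. No statistical figure in the plan depends on it.

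**Working it through.** The plan gives no figure for an untested interval, so there is none to reproduce. The check sets out the schedule and then does interval arithmetic.

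**Scheduled pregnancy tests in the visible text**

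| Time | Test scheduled? | Source |
|---|---|---|
| Screening | Yes | Criterion 6; 4.A1; MRI risk text |
| Baseline scan day | Yes, urine | 4.A.2 |
| Treatment visits 1-10 | No | 4.A.3 |
| Midpoint, week 5 | No | 4.A.4 |
| Post-treatment scan day | Yes, urine | 4.A.2 with 4.A.5 |

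There are no scheduled tests between the two scan days.

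**Inputs.** Treatment length T = 10 to 12 weeks (4.A.3). Midpoint m = week 5 (4.A.4). Delay to study treatment d = 0 to 2 weeks (Research Related Delay to Treatment). Women: 60% of 20 enrolled or of 15 completers (Description of Subject Population).

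**Longest untested interval on treatment.** Now it is T. With a test at week m it is the larger of m and T - m.

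- T = 10, m = 5: larger of 5 and 5 = 5 weeks, a cut of 5/10 = 50%.
- T = 12, m = 5: larger of 5 and 7 = 7 weeks, a cut of 5/12 = 42%.
- T = 12, m = 6 or 7 (visit 5 made up late): 6 or 7 weeks.

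**Start delay.** Assume the baseline scan precedes the first dose by the full two weeks. The interval since the last test is then 2 + 10 = 12 or 2 + 12 = 14 weeks. A week-5 test makes it the larger of 2 + 5 = 7 and T - 5 (5 or 7), so 7 weeks either way.

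**Average wait to the next scheduled test.** Assume a pregnancy becomes detectable at a uniformly random time during dosing. Now the mean wait is T/2 = 5.0 or 6.0 weeks. With a test splitting T into a + b it is (a² + b²)/(2T):

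- 5 + 5: 50/20 = 2.5 weeks.
- 5 + 7: 74/24 = 3.1 weeks.

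**Timing against the dose schedule.** The target is 2.5 mg/day by week 5, and then "Beginning week 6 daily dose will be increased weekly by 0.5 mg/day to a maximum dose of 4mg". That gives 3.0 mg in week 6, 3.5 mg in week 7 and 4.0 mg from week 8, held thereafter. A week-5 result is therefore available before the second phase of increases. If both make-up weeks fall before visit 5, the midpoint moves to week 7, when the calendar schedule is already at 3.5 mg/day. The test then needs a fallback date.

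**Number of tests.** 0.60 × 20 = 12 and 0.60 × 15 = 9. Both are upper figures under the projected sex split: ages run to 60, and the number of women of child-bearing age is not given.

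**The case against.** The strongest reply is that safeguards already exist. Women planning pregnancy are excluded, and tests bracket the treatment. The same psychiatrist sees each patient at all ten visits, with systematic adverse-event queries and 24-hour cover. Further laboratory work is allowed for cause. All of this is true and makes the gap less serious, but it permits a test without scheduling one and gives no instruction about the drug. The nearest withdrawal criterion, inter-current illness, applies only if it prevents compliance. It would also remove the patient from the study, and with that from PE as a study treatment, although the plan calls PE first-line for PTSD.

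A second reply is that the plan does not say why pregnancy is excluded. After screening, every pregnancy step sits under MRI, and the pramipexole risk section states no fetal risk. That stands: the point rests on the plan's own exclusion and not on drug data. But criterion 6 is separate from the MRI exclusions and reaches plans for pregnancy throughout the study, so it is fairly read as covering the treatment period.

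A third is that the consent pages and protocol 7094R may contain contraception or pregnancy instructions. That also stands and limits the point to the text seen.

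A reader might go further in four ways that the documents do not support:

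- **That the dose is raised throughout the 10-12 weeks.** The calendar schedule reaches its maximum at week 8, and increases stop earlier on remission or poor tolerance.
- **That risk to a pregnancy grows with dose.** No section says so.
- **That pramipexole must be barred in the six months of open treatment under item (g).** That is post-study care decided on clinical indication.
- **That naming urine in some places and blood in others for screening is a contradiction.** Both tests may be done.

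**Conclusion.** The point holds as a moderate safety-monitoring recommendation. In the visible text, pregnancy is excluded for the study period, no test is scheduled between the two scan days, and neither the dose rule nor the stop rule covers pregnancy. One midpoint test cuts the longest untested interval on treatment from 10-12 weeks to about 5-7. Under the uniform-onset assumption, the mean wait to a scheduled test falls from 5-6 weeks to 2.5-3.1.

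These figures assume the stated week-5 midpoint, or the fallback date if visit 5 slips. The gap is shortened, not closed. With no pregnancy rate or fetal-risk information in the documents, neither the expected number of pregnancies nor the harm avoided can be estimated, and none is claimed. A reader might infer that pregnancy monitoring is absent altogether. It is not: the tests at screening and on both scan days are clear, and the gap lies within treatment.

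**What to change.** 1. In 4.A.4, add a urine pregnancy test for women of child-bearing age at the midpoint visit, read before any dose above 2.5 mg/day. If visit 5 has slipped, do the test at the psychiatrist visit before the first such dose.
2. In the drug rules of 4.A.3 and item (a) of the pramipexole risk measures, add: after a positive pregnancy test pramipexole is not increased and study dosing is stopped with a supervised taper as in item (f); PE and clinical assessments may continue. Place this with the drug rules and not among the study-withdrawal criteria, so that PE and outcome data are kept.
3. Before finalizing, check the consent form and protocol 7094R for existing pregnancy wording and align with it.

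The cost is at most about 9-12 urine tests, using a test the trial already performs at a visit it already holds, plus a few sentences. No visit, blood draw or change of sample size is needed. A woman who tests positive loses her remaining study dosing. Her post-treatment scan would already be cancelled under the existing MRI text, so the change costs no additional scan.
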